6.1.1. Administration

On Day 1 of each period each participant will receive either tafamidis 12.2 mg tablet under fasting (Treatment A) or fed (Treatment C) conditions or tafamidis meglumine 20 mg soft gelatin capsule (Treatment B) under fasting conditions.

Following an overnight fast of at least 10 hours, participants will receive study intervention at approximately 0800 hours (plus or minus 2 hours). Participants being administered the investigational product in the fed state should start a high-fat/high-calorie breakfast (as per the description in Section 5.3.1) approximately 30 minutes prior to administration of the treatment. The breakfast will be consumed over approximately 25 minutes and investigational product administered within approximately 5 minutes after completion of the meal. Investigator site personnel will administer study intervention during each period with ambient temperature water to a total volume of approximately 240 mL. Participants will swallow the study intervention whole, and will not manipulate or chew the study intervention prior to swallowing.

In order to standardize the conditions on PK sampling days, all participants will be required to refrain from lying down (except when required for BP, pulse rate, and ECG measurements), eating, and drinking beverages other than water during the first 4 hours after dosing.

6.2. Preparation, Handling, Storage, and Accountability

1. The investigator or designee must confirm that appropriate conditions (eg, temperature) have been maintained during transit for all study interventions received and any discrepancies are reported and resolved before use of the study intervention.
2. Only participants enrolled in the study may receive study intervention and only authorized site staff may supply, prepare, and/or administer study intervention.
3. All study interventions must be stored in a secure, environmentally controlled, and monitored (manual or automated recording) area in accordance with the labeled storage conditions with access limited to the investigator and authorized site staff. At

PFIZER CONFIDENTIAL

a minimum, daily minimum and maximum temperatures for all site storage locations must be documented and available upon request. Data for nonworking days must indicate the minimum and maximum temperatures since previously documented upon return to business.

4. Any excursions from the study intervention label storage conditions should be reported to Pfizer upon discovery along with actions taken. The site should actively pursue options for returning the study intervention to the labeled storage conditions, as soon as possible. Once an excursion is identified, the study intervention must be quarantined and not used until Pfizer provides permission to use the study intervention. Specific details regarding the excursion definition and information to report for each excursion will be provided to the site in the IPM.
5. Any storage conditions stated in the SRSD will be superseded by the storage conditions stated on the label.
6. Study interventions should be stored in their original containers.
7. The investigator, institution, head of the medical institution (where applicable), or authorized site staff is responsible for study intervention accountability, reconciliation, and record maintenance (ie, receipt, reconciliation, and final disposition records), such as the IPAL or sponsor-approved equivalent. All study interventions will be accounted for using a study intervention accountability form/record.
8. Further guidance and information for the final disposition of unused study interventions are provided in the IPM. All destruction must be adequately documented. If destruction is authorized to take place at the investigator site, the investigator must ensure that the materials are destroyed in compliance with applicable environmental regulations, institutional policy, and any special instructions provided by Pfizer.
9. All pivotal BA/BE retains should be stored by the investigator site or with a third party vendor. Sample retention is the responsibility of the entity performing the BA/BE study.

Upon identification of a product complaint, notify the sponsor within 1 business day of discovery as described in the IPM.

6.2.1. Preparation and Dispensing

Within this protocol, preparation refers to the investigator site activities performed to make the study intervention ready for administration or dispensing to the participant by qualified staff. Dispensing is defined as the provision of study intervention, concomitant treatments, and accompanying information by qualified staff member(s) to a healthcare provider, participant, in accordance with this protocol. Local health authority regulations or investigator site guidelines may use alternative terms for these activities.

Tablets and capsules will be prepared at the CRU in the individual dosing containers by 2 operators, 1 of whom is an appropriately qualified and experienced member of the study staff (eg, physician, nurse, physician's assistant, nurse practitioner, pharmacy assistant/technician, or pharmacist). The tablets and capsules will be provided in unit dose containers and labeled in accordance with Pfizer regulations and the clinical site's labeling requirements.

6.3. Assignment to Study Intervention

The investigator will assign participant numbers to the participants as they are screened for the study. Pfizer will provide a randomization schedule to the investigator and, in accordance with the randomization numbers, the participant will receive the study treatment regimen assigned to the corresponding randomization number.

The investigator's knowledge of the treatment should not influence the decision to enroll a particular participant or affect the order in which participants are enrolled.

6.4. Blinding

This is an open-label study.

6.4.1. Blinding of Participants

Participants will be unblinded to their assigned study intervention.

6.4.2. Blinding of Site Personnel

Investigators and other site staff will be unblinded to participants' assigned study intervention.

6.4.3. Blinding of the Sponsor

Sponsor staff will be unblinded to participants' assigned study intervention.

6.5. Study Intervention Compliance

Participants will receive study intervention directly from the investigator or designee, under medical supervision. The date and time of each dose administered in the clinic will be recorded in the source documents and recorded in the CRF. The dose of study intervention and study participant identification will be confirmed at the time of dosing by a member of the study site staff other than the person administering the study intervention. Study site personnel will examine each participant's mouth to ensure that the study intervention was ingested.

6.6. Dose Modification

As this is a single-dose study, no dose modification is permitted.

6.7. Continued Access to Study Intervention After the End of the Study

No study intervention will be provided to participants at the end of their study participation.

6.8. Treatment of Overdose

For this study, any dose of PF-06291826 greater than 20 mg tafamidis meglumine or 12.2 mg tafamidis free acid within a 24-hour time period will be considered an overdose.

There is no specific treatment for an overdose.

In the event of an overdose, the investigator should:

1. Contact the study medical monitor within 24 hours.
2. Closely monitor the participant for any AEs/SAEs and laboratory abnormalities as medically appropriate and at least until the next scheduled follow-up.
3. Document the quantity of the excess dose as well as the duration of the overdose in the CRF.
4. Overdose is reportable to Pfizer Safety **only when associated with an SAE**.
5. Obtain a blood sample for PK analysis within 1 day from the date of the last dose of study intervention if requested by the study medical monitor (determined on a case-by-case basis).

6.9. Prior and Concomitant Therapy

Use of prescription or nonprescription drugs and dietary and herbal supplements are prohibited within 7 days or 5 half-lives (whichever is longer) prior to the first dose of study intervention. Limited use of nonprescription medications that are not believed to affect participant safety or the overall results of the study may be permitted on a case-by-case basis following approval by the sponsor. Acetaminophen/paracetamol may be used at doses of ≤ 1 g/day.

Females taking hormone replacement therapy may be eligible to participate in this study if they are willing to discontinue therapy at least 28 days prior to the first dose of study treatment and remain off hormonal therapy for the duration of the study.

All concomitant treatments taken during the study must be recorded with indication, daily dose, and start and stop dates of administration. All participants will be questioned about concomitant treatment at each clinic visit.

Treatments taken within 28 days before the first dose of study intervention will be documented as a prior treatment. Treatments taken after the first dose of study intervention will be documented as concomitant treatments.

7. DISCONTINUATION OF STUDY INTERVENTION AND PARTICIPANT DISCONTINUATION/WITHDRAWAL

7.1. Discontinuation of Study Intervention

Since this is a single-dose study, this section is not applicable.

7.1.1. ECG Changes

If a clinically significant finding is identified (including, but not limited to, changes from baseline in QTcF after enrollment), the investigator or qualified designee will determine if the participant can continue in the study and if any change in participant management is needed. This review of the ECG printed at the time of collection must be documented. Any new clinically relevant finding should be reported as an AE.

7.1.2. COVID-19

If a participant is diagnosed with COVID-19 during the study, it should be reported as an AE or SAE (as appropriate) and appropriate medical intervention should be provided.

7.2. Participant Discontinuation/Withdrawal From the Study

A participant may withdraw from the study at any time at their own request. Reasons for discontinuation from the study include the following:

- Refused further follow-up
- Lost to follow-up
- Death
- Study terminated by Sponsor

At the time of discontinuing from the study, if possible, an early discontinuation visit should be conducted. See the [SoA](#) for assessments to be collected at the time of study discontinuation and follow-up and for any further evaluations that need to be completed.

The early discontinuation visit applies only to participants who are enrolled/randomized and then are prematurely withdrawn from the study. Participants should be questioned regarding their reason for withdrawal.

If a participant withdraws from the study, they may request destruction of any remaining samples taken and not tested, and the investigator must document any such requests in the site study records and notify the sponsor accordingly.

If the participant withdraws from the study and also withdraws consent (see [Section 7.2.1](#)) for disclosure of future information, no further evaluations will be performed and no additional data will be collected. The sponsor may retain and continue to use any data collected before such withdrawal of consent.

7.2.1. Withdrawal of Consent

Participants who request to discontinue receipt of study intervention will remain in the study and must continue to be followed for protocol-specified follow-up procedures. The only exception to this is when a participant specifically withdraws consent for any further contact with them or persons previously authorized by the participant to provide this information. Participants should notify the investigator in writing of the decision to withdraw consent from future follow-up, whenever possible. The withdrawal of consent should be explained in detail in the medical records by the investigator, as to whether the withdrawal is only from further receipt of study intervention or also from study procedures and/or posttreatment study follow-up, and entered on the appropriate CRF page. In the event that vital status (whether the participant is alive or dead) is being measured, publicly available information should be used to determine vital status only as appropriately directed in accordance with local law.

7.3. Lost to Follow-up

A participant will be considered lost to follow-up if the participant repeatedly fails to return for scheduled visits and is unable to be contacted by the study site.

The following actions must be taken if a participant fails to return to the clinic for a required study visit:

- The site must attempt to contact the participant and reschedule the missed visit as soon as possible. Counsel the participant on the importance of maintaining the assigned visit schedule and ascertain whether the participant wishes to and/or should continue in the study;
- Before a participant is deemed lost to follow-up, the investigator or designee must make every effort to regain contact with the participant (where possible, 3 telephone calls and, if necessary, a certified letter to the participant's last known mailing address or local equivalent methods). These contact attempts should be documented in the participant's medical record;
- Should the participant continue to be unreachable, the participant will be considered to have withdrawn from the study.

8. STUDY ASSESSMENTS AND PROCEDURES

8.1. Administrative and Baseline Procedures

The investigator (or an appropriate delegate at the investigator site) must obtain a signed and dated ICD before performing any study-specific procedures.

Study procedures and their timing are summarized in the [SoA](#). Protocol waivers or exemptions are not allowed.

Adherence to the study design requirements, including those specified in the [SoA](#), is essential and required for study conduct.

All screening evaluations must be completed and reviewed to confirm that potential participants meet all eligibility criteria. The investigator will maintain a screening log to

PFIZER CONFIDENTIAL

record details of all participants screened and to confirm eligibility or record reasons for screening failure, as applicable.

Participants will be screened within 28 days prior to administration of the study intervention to confirm that they meet the study population criteria for the study. If the time between screening and dosing exceeds 28 days as a result of unexpected delays (eg, delayed drug shipment), then participants do not require rescreening if the laboratory results obtained prior to first dose administration meet eligibility criteria.

A participant who qualified for this protocol but did not enroll from an earlier cohort/group may be used in a subsequent cohort/group without rescreening, provided laboratory results obtained prior to the first dose administration meet eligibility criteria for this study. In addition, other clinical assessments or specimen collections, eg, retained research samples, may be used without repeat collection, as appropriate.

Every effort should be made to ensure that protocol-required tests and procedures are completed as described. However, it is anticipated that from time to time there may be circumstances outside the control of the investigator that make it unfeasible to perform the test. In these cases, the investigator must take all steps necessary to ensure the safety and well-being of the participant. When a protocol-required test cannot be performed, the investigator will document the reason for the missed test and any corrective and preventive actions that they have taken to ensure that required processes are adhered to as soon as possible. The study team must be informed of these incidents in a timely manner.

If an IV catheter is utilized for blood sample collections, ECGs and vital sign assessments (pulse rate and BP) should be collected prior to the insertion of the catheter.

For samples being collected and shipped, detailed collection, processing, storage, and shipment instructions and contact information will be provided to the investigator site prior to initiation of the study.

The total blood sampling volume for individual participants in this study is approximately 228 mL. The actual collection times of blood sampling may change. Additional blood samples may be taken for safety assessments at times specified by Pfizer, provided the total volume taken during the study does not exceed 550 mL during any period of 56 consecutive days.

To prepare for study participation, participants will be instructed on the information in the [Lifestyle Considerations](#) and [Prior and Concomitant Therapy](#) sections of the protocol.

[figure not shown]
8.2. Efficacy Assessments

Analysis of efficacy is not applicable to this study.

[figure not shown]
CCI

CCI

[figure not shown]
CCI
CCI

8.3.5. COVID-19 Specific Assessments

Participants will be tested for COVID-19 infection per local site procedures prior to being admitted to the clinic for confinement and a subsequent COVID-19 test will be performed after 4 days (ie, upon completion of 4 × 24 hours in house), or if they develop COVID-19-like symptoms. Additional testing may be required by local regulations or by the PI.

[figure not shown]
[figure not shown]
[figure not shown]
[figure not shown]
CCI

[figure not shown]
[figure not shown]
[figure not shown]
CCI

[figure not shown]
CCI

[figure not shown]
CCI

CCI

CCI

- CCI

8.5. Pharmacokinetics

8.5.1. Plasma for Analysis of Tafamidis

Blood samples of approximately 4 mL, to provide approximately 1.5 mL, will be collected for measurement of plasma concentrations of tafamidis as specified in the SoA. Instructions for the collection and handling of biological samples will be provided in the laboratory manual or by the sponsor. The actual date and time (24-hour clock time) of each sample will be recorded.

The actual times may change, but the number of samples will remain the same. All efforts will be made to obtain the samples at the exact nominal time relative to dosing. Collection of samples up to and including 10 hours after dose administration that are obtained within 10% of the nominal time relative to dosing (eg, within 6 minutes of a 60-minute sample) will not be captured as a protocol deviation, as long as the exact time of the collection is noted on the source document and the CRF/DCT. Collection of samples more than 10 hours after dose administration that are obtained \leq 1 hour away from the nominal time relative to dosing will not be captured as a protocol deviation, as long as the exact time of the collection is noted on the source document and the CRF/DCT. This protocol deviation window does not apply to samples to be collected more than 10 hours after dose administration at outpatient/follow-up visits with visit windows.

CCI

Genetic analyses will not be performed on these plasma samples. Participant confidentiality will be maintained.

Samples collected for measurement of plasma concentrations of tafamidis will be analyzed using a validated analytical method in compliance with applicable SOPs.

The PK samples must be processed and shipped as indicated in the instructions provided to the investigator site to maintain sample integrity. Any deviations from the PK sample handling procedure (eg, sample collection and processing steps, interim storage or shipping conditions), including any actions taken, must be documented and reported to the sponsor. On a case-by-case basis, the sponsor may make a determination as to whether sample integrity has been compromised.

8.6. Genetics

8.6.1. Specified Genetics

Specified genetic analyses are not evaluated in this study.

CC1 [REDACTED]

[REDACTED]

[REDACTED]

[REDACTED]

[REDACTED]

8.7. Biomarkers

Biomarkers are not evaluated in this study.

8.7.1. Specified Gene Expression (RNA) Research

Specified gene expression (RNA) research is not included in this study.

8.7.2. Specified Protein Research

Specified protein research is not included in this study.

8.7.3. Specified Metabolomic Research

Specified metabolomic research is not included in this study.

8.8. Immunogenicity Assessments

Immunogenicity assessments are not included in this study.

8.9. Health Economics

Health economics/medical resource utilization and health economics parameters are not evaluated in this study.

9. STATISTICAL CONSIDERATIONS

Detailed methodology for summary and statistical analyses of the data collected in this study is outlined here and further detailed in the SAP, which will be maintained by the sponsor. The SAP may modify what is outlined in the protocol where appropriate; however, any major modifications of the primary endpoint definitions or their analyses will also be reflected in a protocol amendment.

9.1. Statistical Hypotheses

The alternative hypothesis of bioequivalence ($H_1: q_L \leq m_T - m_R \leq q_U$), and the null hypothesis of inequivalence ($H_0: m_T - m_R < q_L$ or $m_T - m_R > q_U$) can be expressed as the following 2 separate one-sided hypotheses:

$$H_{0A}: m_T - m_R < q_L$$

$$H_{1A}: q_L \leq m_T - m_R$$

$$H_{0B}: m_T - m_R > q_U$$

$$H_{1B}: m_T - m_R \leq q_U$$

where m_T and m_R represent the average bioavailability on a log scale for the Test and Reference products respectively and $[q_L, q_U]$ defines the bioequivalence range.

Bioequivalence of the Test treatment to Reference treatment will be concluded if the 90% confidence intervals for the ratios of adjusted geometric means for tafamidis AUC_{inf} (if data permit, otherwise AUC_{last}) and C_{max} fall entirely within the acceptance region of (80%, 125%).

9.2. Analysis Sets

For purposes of analysis, the following analysis sets are defined:

Participant Analysis Set	Description
Enrolled	“Enrolled” means a participant’s, or their legally authorized representative’s, agreement to participate in a clinical study following completion of the informed consent process and randomization/assignment to study intervention. A participant will be considered enrolled if the informed consent is not withdrawn prior to participating in any study activity after screening. Potential participants who are screened for the purpose of determining eligibility for the study, but do not participate in the study, are not considered enrolled, unless otherwise specified by the protocol.

Participant Analysis Set	Description
Full analysis set	Example: All participants randomly assigned to study intervention and who take at least 1 dose of study intervention.
CCI	[REDACTED]
PK Concentration	The PK concentration population is defined as all participants who receive at least 1 dose of tafamidis and who have at least 1 measurable concentration of tafamidis.
CCI	[REDACTED]

9.3. Statistical Analyses

The SAP will be developed and finalized before any analyses are performed and will describe the analyses and procedures for accounting for missing, unused, and spurious data. This section is a summary of the planned statistical analyses of the primary and secondary endpoints.

9.3.1. Pharmacokinetic Analyses

9.3.1.1. Derivation of Pharmacokinetic Parameters

Plasma PK parameters for tafamidis will be derived (as data permit) from the concentration-time data using standard noncompartmental methods as outlined in Table 4. Actual PK sampling times will be used in the derivation of PK parameters. In the case that actual PK sampling times are not available, nominal PK sampling time will be used in the derivation of PK parameters.

Table 4. Plasma Tafamidis Pharmacokinetic Parameters Definitions

Parameter	Definition	Method of Determination
AUC _{last}	Area under the concentration-time curve from 0 to time of last measurable concentration	Linear/Log trapezoidal method
AUC _{inf}	Area under the concentration-time curve from time 0 to infinity	$AUC_{(0-t_{last})} + (C_{last}^*/k_{el})$, where C_{last}^* is the estimated plasma concentration at the last quantifiable time point (C_{last}) estimated from the log-linear regression analysis $C_{last}^* = C_{last} \times e^{(-K_{EL} \times t_{last})}$
CCI	[REDACTED]	[REDACTED]

Table 4. Plasma Tafamidis Pharmacokinetic Parameters Definitions

*if data permit

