4. STUDY DESIGN

4.1. Overall Design

This study will be a Phase 1, open label, randomized, 3-way crossover, single dose study to determine the bioequivalence of PF-06291826 (tafamidis) 12.2 mg tafamidis free acid tablets versus commercial 20 mg tafamidis meglumine capsules administered under fasted conditions and to estimate the effect of food on the 12.2 mg tafamidis free acid tablet in healthy participants.

Screening evaluation will occur within 28 days prior to the first dose in Period 1.

Participants will be admitted to the CRU at least 12 hours prior to dosing on Day 1 and will be required to stay in the CRU for 8 days in each period. A total of 22 participants will be enrolled to ensure a minimum of 18 completers. Participants withdrawn from the study may be replaced. Each period will be separated by a washout of at least 16 days between administration of study drug. On Day 1 of each period, participants will receive a single dose of one of the two tafamidis formulations according to the study schema provided in Table 2. Participants are to be fasted 10 hours prior to dosing (excluding fed arm) and 4 hours post-dosing. For the administration, the drug products will be administrated with 240 mL of

water. Medication will be administered at approximately 8:00 AM \pm 2 hours on Day 1 of each period according to a computer-generated randomization schedule.

Participants will be randomized to receive one of the treatment sequences shown in Table 2:

Table 2. B3461103 Treatment Sequence Schema

Sequence	Period 1	Period 2	Period 3 (Fed)
1 (n = 11)	A	B	C
2 (n = 11)	B	A	C

The study medications are listed in Table 3.

Table 3. Description of Tafamidis Treatment

Treatment	Study Medication
A	12.2 mg tafamidis free acid tablet, fasted (Test)
B	Commercial 20 mg tafamidis meglumine soft gelatin capsule, fasted (Reference)
C	12.2 mg tafamidis free acid tablet, fed

The 12.2 mg tafamidis free acid tablet and commercial 20 mg tafamidis meglumine capsules will be supplied by Pfizer Worldwide Research and Development.

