Appendix 2. List of Abbreviations

Abbreviation	Term
%CV	coefficient of variation
AE	adverse event
CCI	
AUC _{inf}	area under the concentration-time curve from time 0 to infinity
AUC _{last}	area under the concentration-time curve from 0 to time of last measurable concentration
AUMC _{inf}	area under the first moment curve from zero time to infinity
BLQ	below the limit of quantitation
BP	blood pressure
CaPS	Clinical Data Interchange Standards Consortium and Pfizer Standards
CI	confidence interval
C _{last}	estimated plasma concentration at the last quantifiable time point estimated from the log-linear regression analysis
C _{max}	maximum observed plasma concentration
CSR	clinical study report
ECG	electrocardiogram
HR	heart rate
k _{el}	the terminal phase rate constant calculated by a linear regression of the loglinear concentration-time curve
LLQ	lower limit of quantitation
mg	milligram
m _R	the average bioavailability on a log scale for the Reference product
CCI	
m _T	the average bioavailability on a log scale for the Test product
N/A	not applicable
NC	not calculated
ND	not done
NS	no sample
PK	pharmacokinetic(s)
PR	pulse rate
q _L	lower limit of bioequivalence
QRS	Combination of Q-, R- and S- wave on an electrocardiogram representing ventricular depolarization
QTc	corrected QT
QTcF	corrected QT (Fridericia method)
q _U	upper limit of bioequivalence
RR	respiratory rate
SAP	statistical analysis plan
SD	standard deviation
SoA	schedule of activities

Abbreviation	Term
cc	[REDACTED]
TEAE	treatment emergent adverse event
t_{last}	time of last measurable concentration
CCI	[REDACTED]

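### Protocol Table 4: the formula printed for C_last* contradicts its definition in words in the same cell, within the derivation of the primary endpoint AUCinf

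*Protocol*

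**What the plan says.** Protocol Section 9.3.1.1 derives the plasma PK parameters by "standard noncompartmental methods as outlined in Table 4", so Table 4 is the operative definition. Its AUCinf row contains three statements:

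- AUCinf is "AUC_{(0-t_{last})} + (C_{last}^*/k_{el" (closing brackets cut off here), that is, the area to t_last plus C_last*/kel.
- In words, C_last* "is the estimated plasma concentration at the last quantifiable time point (C_{last}) estimated from the log-linear regression analysis".
- As a formula, "C_{last}^* = C_{last} \times e^{(-K_{EL} \times t_{last" (closing brackets again cut off), that is, C_last x exp(-KEL x t_last).

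AUCinf is a primary endpoint together with C_max, with AUClast as the fallback (Protocol Section 3; SAP Section 2.2). SAP Section 2.1 lists no modifications to the protocol's analysis plan. The readable SAP text contains no formula for this quantity. SAP Appendix 2 gives a C_last entry with nearly the same words: "estimated plasma concentration at the last quantifiable time point estimated from the log-linear regression analysis".

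**The concern.** The regression-predicted concentration at t_last is an intercept at time zero, decayed over t_last. The printed formula has C_last where the intercept should stand. The cell itself ties C_last to the last quantifiable time point, so the decay is applied twice. If C_last lies on the fitted line, the result is the concentration at 2 x t_last, or 336 h when the last quantifiable sample is the one at 168 h.

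Programmed literally, the formula would make the extrapolated area too small. AUCinf and its extrapolated share would be too low in the descriptive summaries. AUCinf also enters both the bioequivalence and the food-effect comparisons, so the effect on the ratio needs checking as well.

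**Working it through.** **Inputs from the documents.** The three Table 4 statements above; last planned sample at 168 h (PK sampling schema, Protocol Section 1.3); washout of at least 16 days, or 384 h (Section 4.1); planning ratio 0.9, within-participant SD 0.098 for log AUCinf and a minimum of 18 evaluable participants (Section 9.5). The plan states no figure that depends on this formula, so there is none to reproduce.

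**Assumptions.** The documents give no half-life. I use 24 to 76.8 h, the top being 384 h / 5, where five half-lives per washout is my assumption. Decline is mono-exponential and t_last = 168 h.

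**Step 1, algebra.** The terminal regression is ln C(t) = ln C0* - kel x t, where C0* is the back-extrapolated intercept.

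- By the words: C_last* = C0* x exp(-kel x t_last).
- As printed: C_last* = C_last x exp(-kel x t_last). With C_last on the line, this is C0* x exp(-2 x kel x t_last).

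The two agree only if exp(-kel x t_last) = 1 or if C_last means C0*.

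**Step 2, absolute AUCinf under literal use.** Let f = exp(-kel x 168) = 2^(-168/half-life). Taking the correct AUCinf as 1, the area to t_last is 1 - f, the correct tail is f and the printed tail is f^2. Hence

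AUCinf(printed)/AUCinf(correct) = 1 - f + f^2, and the understatement is f - f^2.

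| Half-life (h) | f | f^2 | Understatement |
|---|---|---|---|
| 24 | 0.0078 | 0.0001 | 0.8% |
| 36 | 0.0394 | 0.0016 | 3.8% |
| 48 | 0.0884 | 0.0078 | 8.1% |
| 60 | 0.1436 | 0.0206 | 12.3% |
| 72 | 0.1984 | 0.0394 | 15.9% |
| 76.8 | 0.2195 | 0.0482 | 17.1% |

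A one-compartment oral profile (assumed ka = 1/h) with the protocol's sampling times and the linear/log trapezoidal rule gives 0.80, 3.86, 8.18, 12.45, 16.07 and 17.30%. At 48 h the extrapolated share falls from 9.0% to 0.9%. With the intercept in place of C_last, AUCinf agrees with the analytic value to about 0.1% (69.20 against 69.25 at 48 h).

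**Step 3, C_last as an observed value off the line.** If C_last = (1 + e) x fitted value, the understatement is f - (1 + e) x f^2. At 76.8 h, e = +20% gives 16.2% and e = -20% gives 18.1%.

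**Step 4, the Test/Reference ratio.** Write g(f) = 1 - f + f^2. The ratio is multiplied by g(f_T)/g(f_R), where f_T and f_R are the values of f for Test and Reference.

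- Equal kel and t_last: the factor is 1. In the oral profile, with different assumed ka (0.7 Test, 1.0 Reference) and a true ratio of 0.900, the printed formula gives 0.8993 to 0.8997 at half-lives of 36 to 72 h.
- Test kel 10% lower in every participant: largest shift at a half-life of about 64 h, where f_R = 0.162 and f_T = 0.195, so 0.8432/0.8640 - 1 = -2.41%.
- Test kel 10% higher: at most +2.23%. For 5% differences: at most -1.18% or +1.14%.

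**Step 5, against the acceptance limit.** The expected 90% half-width on the log scale is t(0.95, 16) x 0.098 x sqrt(2/18) = 1.746 x 0.098 x 0.3333 = 0.0570. The expected lower limit is 0.9 x exp(-0.0570) = 0.850. After the worst shift in Step 4 it is 0.850 x (1 - 0.0241) = 0.830, still above 0.80.

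**The case against.** The point rests on one symbol in a table read from PDF by a program. Table 4 is partly redacted, and nearby symbols are rendered inconsistently (k_el and K_EL in the same cell). The protocol's abbreviation list has no C_last entry, so its meaning is inferred from the cell, and a redacted row could hold a definition. A pharmacokineticist would follow the words and the instruction to use standard methods. The decision rests on a ratio in which the error nearly cancels, and AUClast, which does not use the formula, is analysed in any case. The half-lives are assumed.

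Most of this stands. The source page must be checked first, literal use is unlikely, and no effect on the conclusion is shown. The mismatch itself remains. The extracted text keeps starred and unstarred C_last apart within the cell, and no readable passage makes the unstarred symbol an intercept. A formula that must be ignored to obtain the right result should not stay in the table that defines a primary endpoint. The SAP does not settle the matter either way: parts are redacted and may contain the derivation, and its C_last entry may be the starred quantity with the asterisk lost.

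**Conclusion.** The concern holds as a minor point. As the text reads, the Table 4 formula for C_last* is wrong and the definition in words is right, subject to confirming the symbol on the source page. The size is conditional on literal programming: absolute AUCinf too low by 0.8% to 17.1% over the assumed half-lives, with the Test/Reference ratio unchanged for equal kel and t_last and shifted by at most 2.4% for a uniform 10% difference in kel. The stated sample size and power do not depend on the formula.

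**What to change.** 1. Check the AUCinf row of Table 4 on the source page for a misread symbol.
2. If the formula is as printed, either delete it and keep the words, or replace it with C_last* = C0* x exp(-kel x t_last), defining C0* as the back-extrapolated time-zero intercept of the terminal log-linear regression.
3. Confirm that any derivation in the redacted SAP text, and the C_last entry in SAP Appendix 2, use the same symbol and definition.

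The cost is a one-line correction and a consistency check of the SAP. Nothing operational changes.
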